5. ASSESSMENT OF SAFETY

The Principal Investigator is responsible for ensuring that all staff involved in the study is familiar with the content of this section.

5.1 Safety parameters

5.1.1 Definition of adverse events

The International Conference on Harmonization (ICH) Guideline for Good Clinical Practice (GCP) E6(R2) defines an adverse event (AE) as:

Any untoward medical occurrence in a patient or clinical investigation patient administered a pharmaceutical product and which does not necessarily have a causal relationship with this treatment. An AE can, therefore, be any unfavorable and unintended sign (including an abnormal laboratory finding), symptom, or disease temporally associated with the use of a medicinal product, whether or not considered related to the medicinal product.

An AE includes but is not limited to any clinically significant worsening of a patient's pre-existing condition. An abnormal laboratory finding (including ECG finding) that requires an action or intervention by the investigator, or a finding judged by the investigator to represent a change beyond the range of normal physiologic fluctuation, should be reported as an AE.

AEs may be treatment emergent (i.e., occurring after initial receipt of investigational product) or non-treatment emergent. A non-treatment-emergent AE is any new sign or symptom, disease, or other untoward medical event that begins after written informed consent has been obtained but before the patient has received investigational product.

Elective treatment or surgery or preplanned treatment or surgery (that was scheduled prior to the patient being enrolled into the study) for a documented pre-existing condition, that did not worsen from baseline, is not considered an AE (serious or non-serious). An untoward medical event occurring during the prescheduled elective procedure or routinely scheduled treatment should be recorded as an AE or serious (S)AE.

The term AE is used to include both serious and non-serious AEs.

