
Study Products
	
Methylprednisolone succinate and prednisone (Corticosteroids, CS) Dapagliflozin (Sodium-glucose cotransporter 2 inhibitor, SGLT2i)

Treatments
	
ACiGaN Study
 
IgAN Active renal lesions
 
Experimental arm: Corticosteroids + RASBs (4 months) → RASBs (4 months) → RASBs (28 months)
 
Control arm (KDIGO): RASBs (4 months) → RASBs + Corticosteroids (4 months) → RASBs (28 months)
 <hr/> 
CHRONiGaN Study
 
IgAN Chronic renal lesions Moderate renal lesions
 
Experimental arm: RASBs (4 months) → RASBs + Dapagliflozin (6 months) → RASBs + Dapa (26 months)
 
Control arm (KDIGO): Run-in → RASBs + Corticosteroids (6 months) → RASBs (26 months)
 
Patients will be randomized separately in each trial (allocation 1 to 1 ratio). Stratified randomization will be done by age and sex in renal centers.
 
ACiGaN trial
 
Experimental arm: Early corticosteroids therapy combined with RASBs followed by RASBs treatment.
 
Control arm (standard care): RASBs treatment followed by corticosteroids combined with RASBs and then only RASBs.
 
CHRONiGaN trial
 
Experimental arm: RASBs therapy followed by Dapagliflozin combined with RASBs.
 
Control arm (standard care): RASBs therapy followed by Corticosteroids combined with RASBs and then RASBs alone

Sample Size and Statistics
	
ACiGaN. Data from the literature have shown a difference in renal survival between corticosteroids and controls when the researchers assumed a difference of 50% in the primary end point (i.e., in the between-arms difference of delta 24 hour proteinuria from base-line to 6 months) as clinically relevant. Therefore, we assume that a mean delta proteinuria from base-line to 6 months in patients treated with RASBs alone (control arm) is 0.6 ± 1.0 g/24 hours (\pmSD) versus a mean delta proteinuria 1.2 ± 1.0 g/24 hours (\pmSD) from base-line to 6 months in patients treated with RASBs and corticosteroids (experimental arm). Based on these assumptions, we calculated a sample size of 132 patients (66 patients per group including a 10% dropout rate) for a power of 90%, a two-sided significance level of 0.05 and 3 years

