1.2. Rationale

In our CLlIgAN study, we have planned to evaluate:

- (i) The effect of early start corticosteroid therapy combined with RASBs (experimental arm) versus RASBs alone in IgAN patients with active renal lesions (AClIgAN) who will receive corticosteroids after 4 months of RASBs (standard care) in presence of persistent proteinuria ≥ 0.5 g/24 hours and eGFR ≥ 30 ml/min/1.73 m² (control arm).
- (ii) The effect of SGLT2i (dapagliflozin) combined with RASBs (experimental arm) versus corticosteroids combined with RASBs (control arm) in IgAN patients with chronic or moderate renal lesions (CHRONlIgAN) after a run-in phase of 4 months in which they will receive RASB therapy alone (standard care).

In both studies patients enrolled in the control arms will be treated according to the evidence-based recommendations (standard care) provided within the KDIGO guidelines.

In conclusion, we would like to evaluate the effect of early start corticosteroids in IgAN patients with active renal lesions (AClIgAN) and to spare corticosteroids therapy in IgAN with chronic or moderate renal lesions (CHRONlIgAN) administering Dapagliflozin.

We would also provide earlier ESKD risk prediction by using our tool DialCheck (32).

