3. TRIAL DESIGN

This project encompasses two prospective, multicentre, open-label randomized controlled clinical trials (RCTs) of IgAN patients (CLlGaN) based on the kidney biopsy report (*Figure 1*).

Stratified randomization will be done by age and sex in renal centers.

[figure not shown]

Figure 1

ACiGaN TRIAL

Patients with active renal lesions (E1 and/or C1) in the presence of $GFR \geq 30$ ml/min/1.73 m² and proteinuria ≥ 0.5 g/24 hours will be randomized into two arms:

- 1) corticosteroids combined with RASBs for 4 months followed by RASBs alone (experimental arm);
- 2) RASBs alone for 4 months followed by the combination corticosteroids and RASBs for 4 additional months and then only RASBs (standard care) as suggested by KDIGO guidelines (5).

Participants assigned to the experimental arm will receive by 2 weeks from the kidney biopsy (pulse) methylprednisolone (SOLU-Medrol) 500-1000 mg in the first day and then 50% of dose in the next two days followed by oral prednisone (0.5 mg/kg/bw) on alternate days until the end of the month. This treatment will be repeated for three consecutive months. After three months, participants will gradually reduce oral prednisone, in the course of four weeks. Next, they will receive RASBs alone.

The daily dose of methylprednisolone will be individualized (15 mg/kg), based on the ideal body weight. The drug will be administered in a single dose intravenously for 30-60 min. To avoid obesity and diabetes corticosteroids will be administered only in the morning.

This is a parallel group, two arm, superiority trial with 1:1 allocation ratio.

As per standard care RASB therapy will be titrated to its maximum labelled or tolerated dose as anti-proteinuric effect in every patient.

Rationale of the study design

Corticosteroids at high dosage have been administered in RCTs of IgAN (18,41) independent of the type of renal lesions despite empiric evidence from clinical practice and strong and consistent evidence from observational studies that the lesions identified at kidney biopsy may play a role in the response to treatment. Our aim is to evaluate the benefit of early pulse therapy combined with oral prednisone only in IgAN patients with active renal lesions. In our protocol, we have excluded intensive immunosuppressive therapy (CS+CYP/AZA/MMF) because RCTs have demonstrated that the potential benefits-harms trade off is in favour of the harms (42).

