5.3.3 Relationship to protocol procedures

The Investigator is also required to provide an assessment of the relationship of SAEs to protocol procedures on the SAE report form. This includes both non-treatment–emergent (i.e., SAEs that occur prior to the administration of IP) and treatment-emergent SAEs. A protocol-related SAE will be used as a result of a procedure or intervention required during the study (e.g., blood collection). The following guidelines will be used by the investigators to assess the relationship of SAEs to the protocol:

- Protocol related: The event occurred due to a procedure or intervention that has been described in the protocol for which there is no alternative etiology present in the patient’s medical record.

- Not protocol related: The event is related to an etiology other than the procedure or intervention that is described in the protocol. The alternative etiology must be documented in the study patient's medical record.

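### Treatment-emergence is anchored to the first investigational product, which gives ACiGaN no common start in the two arms; an unadjusted treatment-emergent comparison would use unequal windows

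*Protocol*

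**What the plan says.** Section 5.1.1 sets the rule: "AEs may be treatment emergent (i.e., occurring after initial receipt of investigational product) or non-treatment emergent". An event is non-treatment-emergent if it "begins after written informed consent has been obtained but before the patient has received investigational product". Section 5.3.3 carries the split into serious events, describing the non-treatment-emergent ones as "SAEs that occur prior to the administration of IP", and asks for a relationship assessment in both classes.

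The Synopsis lists the study products as "Methylprednisolone succinate and prednisone (Corticosteroids, CS) Dapagliflozin (Sodium-glucose cotransporter 2 inhibitor, SGLT2i"). Section 1.3 covers the same drugs, and RASBs have their own Section 1.4.

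For ACiGaN, Section 3 gives the experimental arm "corticosteroids combined with RASBs for 4 months followed by RASBs alone (experimental arm") and the control arm "RASBs alone for 4 months followed by the combination corticosteroids and RASBs for 4 additional months and then only RASBs". Section 1.2 makes the control steroid course conditional: controls are those "who will receive corticosteroids after 4 months of RASBs (standard care) in presence of persistent proteinuria" at or above 0.5 g/24 hours and with eGFR at or above 30.

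On collection, Sections 5.3 and 5.3.1 record all adverse events from consent to 30 days after last treatment, and Section 5.3.8 reports all serious events. Section 7.4 refers harms to the intention-to-treat population, while Section 6.5 defines a safety population of patients with at least one dose of investigational drug.

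**The concern.** In ACiGaN both arms are planned to receive steroids, and the arms differ in when. A rule that starts the clock at the first dose of the product therefore starts it at different times by design. Read with the listed study products, an infection in month 2 is treatment-emergent in the early-steroid arm and non-treatment-emergent in the control arm. A control who never starts steroids can have no treatment-emergent event in 36 months.

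Harm in the first 4 months is central to the question ACiGaN asks. If a safety table or test were later built on this label without adjusting for time at risk, it would show excess harm for early steroids even with equal true event rates. This comes from the event window, so it persists even if every randomised patient is placed in the safety set.

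**Working it through.** The protocol gives no adverse-event rate and no share of controls who never start steroids. Both are assumptions below, shown over a range.

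**Inputs**
- First listed product, ACiGaN experimental arm: month 0 (Section 3).
- First listed product, ACiGaN control arm: month 4 (Section 3), or never if the Section 1.2 condition is not met.
- Follow-up: 36 months, leaving out the final 30 days (Section 4.5).
- Patients: 66 per arm (Section 6).
- Assumed: one event rate λ per patient-month, constant and equal in both arms; a share q of controls who never start steroids.

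**Step 1. Window lengths, if investigational product means the listed products and q = 0**
- To month 8: 8 − 0 = 8 months v 8 − 4 = 4 months; ratio 8/4 = 2.0.
- To month 36: 36 − 0 = 36 months v 36 − 4 = 32 months; ratio 36/32 = 1.125.

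**Step 2. Patients with at least one treatment-emergent event**

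Experimental arm: 1 − exp(−λ × window). Control arm, all randomised in the denominator: (1 − q) × [1 − exp(−λ × window)]. The false-positive rate is the chance that a two-sided 0.05 two-proportion test with 66 per arm is significant when the true rates are equal.

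| Time | λ | q | Experimental | Control | False-positive rate |
|---|---|---|---|---|---|
| Month 8 | 0.03 | 0 | 1 − exp(−0.24) = 21% | 1 − exp(−0.12) = 11% | 0.34 |
| Month 8 | 0.05 | 0 | 1 − exp(−0.40) = 33% | 1 − exp(−0.20) = 18% | 0.50 |
| Month 8 | 0.10 | 0 | 1 − exp(−0.80) = 55% | 1 − exp(−0.40) = 33% | 0.72 |
| Month 36 | 0.05 | 0 | 1 − exp(−1.80) = 83% | 1 − exp(−1.60) = 80% | 0.08 |
| Month 36 | 0.05 | 0.2 | 83% | 0.8 × 80% = 64% | 0.74 |
| Month 36 | 0.05 | 0.3 | 83% | 0.7 × 80% = 56% | 0.94 |

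The last two rows keep never-starters in the denominator with no countable time. If they are removed, as a population requiring a dose would do on this reading, the control proportion returns to 80%.

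**Step 3. If RASBs are investigational product**

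Both arms are then exposed from month 0 or earlier, so the between-arm artefact is zero. The start is still not clean. Section 4.2.1.1, criterion 6, admits patients already on RASBs, whose initial receipt precedes consent, alongside patients who begin RASBs in the trial. The treatment-emergent period would then depend on prior treatment.

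**Step 4. CHRONiGaN**

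Both arms receive RASBs for 4 months and then their listed product (Section 3). The start is month 4 in each arm, so the planned windows are equal.

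**Step 5. Counting from randomisation**

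The ACiGaN windows become 8 v 8 and 36 v 36 months (ratio 1.0). Equal rates then give equal proportions.

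**The case against.** The strongest reply is that no stated analysis uses the label. Treatment-emergent appears only in Sections 5.1.1 and 5.3.3, the latter covers both classes, and Section 6.4 specifies no treatment-emergent table or test. Collection is symmetric from consent (Sections 5.3, 5.3.1, 5.3.8), and Section 7.4 refers harms to the intention-to-treat population. Safety tabulation may also be settled in an analysis plan that is not shown. This stands. A reader might infer that control events in months 0-4 go uncounted and that the plan therefore creates a false safety difference. The documents do not support that, because those events are recorded and nothing limits the comparison to treatment-emergent ones.

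Second, RASBs may be investigational drugs. Section 4.3.1 lists them first among the study treatments, and Section 1.5 includes their risks among those of study treatment. Section 3 has CHRONiGaN patients receiving study treatments within 4 weeks of biopsy, when only RASBs are given. The 8-month persistence on investigational drugs in Section 6.5 cannot be met by a 4-month steroid course alone. This also stands as a possible reading. It removes the between-arm asymmetry but not the lack of a common start.

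Third, a reader might take the 0.74 and 0.94 at month 36 as the expected size of the problem. They rest on assumed rates and shares, and on pairing an all-randomised denominator with a treatment-emergent numerator, which the protocol never specifies. With all controls starting steroids the figure is 0.08. Rates per person-month at risk would also be equal under a constant rate.

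What remains is that Section 5.1.1 states a rule, which an analysis plan may well inherit, and it gives no clean common start on either reading.

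**Conclusion.** The point holds in conditional form. On the listed-products reading, Section 5.1.1 labels the same early ACiGaN event differently by arm; on the RASB reading, the start may fall before consent. A bias follows only if investigational product excludes RASBs and the arms are compared on treatment-emergent events without adjusting for time at risk. The protocol fixes neither condition.

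Under both conditions the distortion is greatest early. By month 8 it is 33% v 18% at an assumed 0.05 events per patient-month and 21% v 11% at 0.03, with equal true rates. By month 36 it is small (false-positive rate about 0.08 at 0.05) unless never-starters stay in the denominator. The issue is specific to ACiGaN, and correcting it is worthwhile because early steroid harm is part of what that trial compares.

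**What to change.** - In Section 5.1.1, define treatment-emergent in ACiGaN as onset on or after randomisation in both arms, whatever drug is being taken. Use the same rule for serious events in Section 5.3.3.
- Tabulate ACiGaN events by randomised arm over identical windows: 0-4, 4-8 and 0-36 months.
- In CHRONiGaN, use one common start in both arms, for example randomisation, with months 4-36 as a second window.
- State whether RASBs are investigational product.
- Reconcile the dosed safety population in Section 6.5 with the intention-to-treat harms population in Section 7.4. On the listed-products reading, the former drops controls who never start steroids.

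The cost is a few sentences in Sections 5.1.1, 5.3.3, 6.5 and 7.4. No new data are needed, because events are already recorded from consent in both arms, and no dose, schedule or clinical rule changes.

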5.1.2 Definition of serious adverse events

A serious adverse event (SAE) is an AE occurring during any study phase (i.e., screening, run-in, treatment, wash-out, follow-up), at any dose of the study drugs that fulfils one or more of the following criteria:

- Results in death
- Is immediately life-threatening
- Requires in-patient hospitalization or prolongation of existing hospitalization
- Results in persistent or significant disability or incapacity
- Is a congenital abnormality or birth defect in offspring of the patient
- Is an important medical event that may jeopardize the patient or may require medical intervention to prevent one of the outcomes listed above.
 - o Medical or scientific judgment should be exercised in deciding whether expedited reporting is appropriate in this situation. Examples of medically important events are intensive treatment in an emergency room or at home for allergic bronchospasm, blood dyscrasias, or convulsions that do not result in hospitalizations; or development of drug dependency or drug abuse.

The causality of SAEs (their relationship to all study treatment/procedures) will be assessed by the investigator(s) and communicated to the Sponsor.

5.1.3 Definition of adverse drug reactions

An Adverse Drug Reaction (ADR) is a response to a medicinal product which is noxious and unintended. This definition includes noxious and unintended effects resulting not only from the authorised use of a medicinal product at normal doses, but also from medication errors and uses outside the terms of the marketing authorisation, including the overdose, misuse and abuse of the medicinal product.

The definition implies a reasonable possibility of a causal relationship between the event and the IMP. This means that there are facts (evidence) or arguments to suggest a causal relationship.

A “serious” adverse reaction is an adverse reaction considered ‘serious’ according to the criterion of ‘seriousness’ reported in the previous section “Definition of serious adverse events”.

An “unexpected adverse reaction” is defined as ‘an adverse reaction, the nature or severity of which is not consistent with the applicable product information (e.g. investigator’s brochure for an unauthorised investigational product or summary of product characteristics for an unauthorised product)’.

5.2 Assessment of safety parameters

5.2.1 Assessment of severity

Assessment of severity is one of the responsibilities of the investigator in the evaluation of AEs and SAEs.

The determination of severity should be made by the investigator based upon medical judgment and the severity categories of Grade 1 to 5 as defined below.

Grade 1 (mild): An event that is usually transient and may require only minimal treatment or therapeutic intervention. The event does not generally interfere with usual activities of daily living.

Grade 2 (moderate): An event that is usually alleviated with additional specific therapeutic intervention. The event interferes with usual activities of daily living, causing discomfort but poses no significant or permanent risk of harm to the patient.

Grade 3 (severe): An event that requires intensive therapeutic intervention. The event interrupts usual activities of daily living, or significantly affects the clinical status of the patient.

Grade 4 (life-threatening): An event, and/or its immediate sequelae, that is associated with an imminent risk of death or with physical or mental disabilities that affect or limit the ability of the patient to perform activities of daily living (eating, ambulation, toileting, etc).

Grade 5 (fatal): Death (loss of life) as a result of an event.

It is important to distinguish between serious criteria and severity of an AE. Severity is a measure of intensity whereas seriousness is defined by the criteria in the previous section.

A Grade 3 AE need not necessarily be considered an SAE. For example, a Grade 3 headache that persists for several hours may not meet the regulatory definition of an SAE and would be considered a non-serious event, whereas a Grade 2 seizure resulting in a hospital admission would be considered an SAE.

5.2.2 Assessment of relationship

Assessment of relationship to either investigational product or study procedures will be made according to investigator's best judgement.

5.3 Recording of AEs and SAEs

AEs and SAEs will be collected from the time of the patient signing the informed consent form until 30 days after last treatment. If an event that starts post the defined safety follow up period noted above is considered to be due to a late onset toxicity to study drug, then it should be reported as an AE or SAE as applicable.

During the course of the study, all AEs and SAEs should be proactively followed up for each patient for as long as the event is ongoing. Every effort should be made to obtain a resolution for all events, even if the events continue after the patient has discontinued study drug or the study has completed.

Any AEs that are unresolved at the patient's last visit in the study are followed up by the Investigator for as long as medically indicated, but without further recording in the eCRF. Sponsor retains the right to request additional information for any patient with ongoing AE(s)/SAE(s) at the end of the study, if judged necessary.

The following variables will be collected for each AE:

- AE (verbatim)
- The date when the AE started and stopped
- The maximum grade reported
- Changes in grade
- Whether the AE is serious or not
- Investigator causality rating against the investigated products (IPs) (yes or no)
- Action taken with regard to IPs
- Administration of treatment for the AE
- Outcome

In addition, the following variables will be collected for SAEs:

- Date of the AE met criteria for SAE
- Date of the Investigator became aware of the SAE
- Seriousness criteria fulfilled

- Date of hospitalization
- Date of discharge
- Probable cause of death
- Date of death
- Whether an autopsy was performed
- Causality assessment in relation to study procedure(s)
- Causality assessment in relation to other medication, as explained in Section 9.3.2
- Description of the SAE.

5.3.1 Study recording period and follow-up for AEs and SAEs

AEs and SAEs will be recorded from time of signature of informed consent, throughout the treatment period and 30 days after last treatment.

During the course of the study all AEs and SAEs should be proactively followed up for each patient. Every effort should be made to obtain a resolution for all events, even if the events continue after discontinuation/study completion.

The investigator is responsible for following all SAEs until resolution, until the patient returns to baseline status, or until the condition has stabilized with the expectation that it will remain chronic, even if this extends beyond study participation.

